1.1 Background and Rationale

Aneurysmal subarachnoid hemorrhage (aSAH) is relatively frequent, accounting for 5% of strokes, and affects a relatively young population. The most frequent complication of aSAH is arterial vasospasm, with an estimated incidence in the literature as high as 70%. Vasospasm is responsible for delayed cerebral ischemia (DCI) which in turn is responsible for severe morbidity (neurological deficit, neuro psychiatric disorders...), poor quality of life (institutionalization, inability to return to work ...) and increased mortality. Treatment with intravenous (IV) milrinone, an arterial vasodilator, has been proposed, but no randomised controlled trial (RCT) exist. We hypothesized that an IV infusion of milrinone will improve the neurological recovery of patients with vasospasm following aneurysmal aSAH at 3 months. In collaboration with the ATLANREA group and the SFAR research network, we are conducting a multicenter, double blinded RCT to evaluate the effect of IV milrinone infusion compared to placebo on 3-months functional neurologic outcome, in patients with proven vasospasm on a computed tomographic angiography (CTA), following acute aSAH.

1.2 Objectives

1.2.1 Primary objective

The primary objective of this study is to evaluate the effect of intravenous milrinone infusion, as compared with placebo, on functional neurological outcomes at 3 months in patients with arterial vasospasm following acute aSAH.

1.2.2 Secondary objectives:

To evaluate the effect of IV milrinone vs placebo on a) 3 and 6 months overall function; b) 3- and 6-months quality of life, c) mortality.

 CHU ANGERS <small>CENTRE HOSPITALIER UNIVERSITAIRE</small>	 MiVAR Statistical analysis plan	N° EudraCT 2019-002145-37 CT Number : 2024-515994-83-00 SAP V1.0 Date : 15/01/2026
---	--	---

1.2.3 *Tertiary objectives:*

To evaluate the effect of IV milrinone vs placebo on the intensive care unit (ICU) and hospital length of stays, on angiographic success at D7 and D14 (if available), on cerebral necrotic volume assess by magnetic resonance imaging (MRI) between 3 and 6 months following aSAH (if available) and on adverse events.

2 Section 2: Study Methods

2.1 Trial Design

MiVAR is a multi-center, double blinded, randomized, placebo-controlled trial that compares the effect of IV milrinone vs placebo (saline), started within 6 hours of the vasospasm confirmation using an computed tomography angiography (CTA), on 3-months function outcomes, in patients with cerebral vasospasm following aSAH.

2.1.1 *Trial interventions*

Eligible patients are randomly assigned to receive either milrinone or placebo within 6 hours after confirmation of the vasospasm diagnosis on a CTA. Study medications are prepared by unblinded nurses or pharmacists not involved in patients care. The study drugs are diluted according to the patient's body weight, so that infusion rates are identical in the two groups for all patients (i.e. an infusion rate of 10 ml per hour corresponds to 0.1 µg/kg/min of milrinone). Milrinone and saline solution are identical in appearance, thereby ensuring blinding of patients, nurses, physicians and outcome assessors.

- **Milrinone group:** milrinone is administered intravenously as a bolus of 0.1 mg/kg over 30 minutes followed by a continuous infusion at a rate of 1 µg/kg/min. In the absence of improvement, the infusion rate may be increased to 1.5 µg/kg/min.
- **Placebo group:** placebo (normal saline) is administered intravenously at the same infusion rate as milrinone.
- **Both groups:** in both groups, induced hypertension with norepinephrine is recommended, along with maintenance of normovolemia. Oral nimodipine is also recommended through D21 after aSAH. Persistence of vasospasm should be assessed at least twice daily by clinical evaluation and/or transcranial doppler (TCD)

 CHU ANGERS <small>CENTRE HOSPITALIER UNIVERSITAIRE</small>	 Statistical analysis plan	N° EudraCT 2019-002145-37 CT Number : 2024-515994-83-00 SAP V1.0 Date : 15/01/2026
---	--	---

examination. In absence of improvement, arteriography for mechanical and/or pharmacological dilatation is recommended.

Duration of treatments

- Study drug weaning is initiated after 48 hours of infusion, with gradual dose tapering in decrement of 0.5 µg/kg/min steps), once vasospasm is controlled. Study medication is discontinued after 7 days in absence of effect on the D7 CTA or on D14.

2.2 Randomization

Randomization is performed using a web-based system (Clinsight® software). Patients are randomly assigned in a 1:1 ratio to one of the two groups using a minimization algorithm based on three determinants: study site, initial World Federation of Neurological Surgeons (WFNS) grade ([1 or 2] vs [3 to 5], higher scores being indicative of more severe aSAH), state of consciousness at the time of vasospasm diagnosis (conscious vs unconscious, including patients under sedation).

2.3 Sample Size

We estimated that the rate of favorable neurological outcomes (defined as a mRS ≤ 2) at 3 months in patients with vasospasm following acute aSAH without milrinone infusion is approximately 35%. (This percentage was estimated based on the analysis of data extracted from the ATLANREA database, including 436 patients in 3 years, ClinicalTrials.gov - identifiant : NCT02714387) The proportion of favorable outcomes reported in case series of patients with vasospasm treated with milrinone is between 50 and 60%. For our sample size calculation, we thus hypothesized a percentage of favorable outcomes at 3 months of 35 and 50% respectively in the control and milrinone group. Considering a two sided test and a type I and type II error rates of 5 and 20%, the sample size required is 340 (170 patients in each group). Considering a 5% proportion of withdrawals, we planned to include 360 patients, and increased this number to 370 to compensate for patients included but not randomized because of early withdrawal.

 CHU ANGERS <small>CENTRE HOSPITALIER UNIVERSITAIRE</small>	 Statistical analysis plan	N° Eudract 2019-002145-37 CT Number : 2024-515994-83-00 SAP V1.0 Date : 15/01/2026
---	--	---

2.4 Timing of final analysis

Six months after completing the trial enrollment (corresponding to the follow-up of the last patients included), the database will be monitored, cleaned, verified and locked. The publication of this SAP will occur prior to the database lock. Final analysis will commence once the final lock has been confirmed by the principal investigator. Unblinding will only occur once the primary and secondary analyses are complete.

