3.1 Confidence Intervals and P-values

The statistical uncertainty of all estimates will be expressed as two-sided 95% confidence intervals. A p-value will only be reported for all the primary and secondary outcomes. A p-value <0.05 will be considered significant.

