 CHU ANGERS <small>CENTRE HOSPITALIER UNIVERSITAIRE</small>	 Statistical analysis plan	N° EudraCT 2019-002145-37 CT Number : 2024-515994-83-00 SAP V1.0 Date : 15/01/2026
---	--	---

5.2.3 *Tertiary outcomes*

- The analysis of angiographic successes at day 7 and 14 will be performed considering (ordinal) proportional odds models, based on the same set of covariates
- The proportion of therapeutic arteriography between each group and the median number of arteriography will be compared.
- The analysis of hospital length of stay will be carried out by using linear regression models based on the same set of covariates.
- Patients outcomes and treatment tolerance will be analyzed using logistic models for dichotomous data (transfer to a convalescent center, patients living at home at 3 and 6 months, need to initiate or to increase the catecholamine doses by 50%, occurrence of dysnatremia), or linear regression models for continuous data (DAAH90, daily dose of catecholamines, average daily urine output).

5.2.4 *Pre-planned sub-group analysis*

We plan exploratory subgroup analyses for the primary outcome (as described above) in the following sub-groups:

- Sex: female sex versus male sex. We hypothesize no treatment effect difference between male and female sex.
- Initial WFNS score <3 vs ≥ 3 . We hypothesize that the treatment effect is more important in the less severe patients (WFNS <3).
- Consciousness level at inclusion: conscious vs unconscious. We hypothesize that the treatment effect is more important in the less severe patients (conscious patients).

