mRS at 3 month	Log-binomial logistic regression with fixed effects for treatment and, and a random effect for center, initial WFNS (<3 or ≥ 3) and patient's consciousness, reported as a risk ratio with 95% CI	
 Another model adjusted with level of consciousness and delay before performing arteriography (< or \geq 12h) Sub-group analysis Per protocol analysis† Patients without missing data 	
 Proportional odds analysis using the Brant-Wald test 	
 center, initial WFNS (<3 or ≥ 3) patient's consciousness at inclusion
Secondary outcomes				
mRS at 6-months	Log-binomial logistic regression reported as a risk ratio with 95% CI		
 unadjusted model Proportional odds analysis using the Brant-Wald test 	
 center, initial WFNS (<3 or ≥ 3) patient's consciousness at inclusion
GOSE at 3 and 6 months	Linear logistic regression model, reported as mean difference with 95% CI		
 unadjusted model 	
 center, initial WFNS (<3 or ≥ 3) patient's consciousness at inclusion
EQ-5D	Linear logistic regression model, reported as mean difference with 95% CI	
 Excluding deceased patient 	
 unadjusted model 	
 center, initial WFNS (<3 or ≥ 3) patient's consciousness at inclusion
Mortality hospital	Log-binomial logistic regression reported as a risk ratio with 95% CI		
 unadjusted model 	
 center, initial WFNS (<3 or ≥ 3) patient's consciousness at inclusion
Mortality 6 months	
 Kaplan-Meier curves and Cox regression hazard ratios 		
 unadjusted model 	
 center, initial WFNS (<3 or ≥ 3) patient's consciousness at inclusion
Tertiary outcomes				
ICU and Hospital LOS	Presented as median difference with 95% CI, using quantile regression		
 median with IQR unadjusted model 	
 center, initial WFNS (<3 or ≥ 3) patient's consciousness at inclusion

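### Section 2.4 protects the blind only through the primary and secondary analyses, so tertiary and safety analyses, five of them with two named models, may be run with the arms known

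*SAP*

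**What the plan says.** SAP section 2.4 locks the database, then starts the final analysis, and sets this condition on opening the code: "Unblinding will only occur once the primary and secondary analyses are complete". It also commits that "The publication of this SAP will occur prior to the database lock". Section 3.1 limits formal testing: "A p-value will only be reported for all the primary and secondary outcomes". All estimates carry two-sided 95% confidence intervals.

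The SAP uses primary, secondary and tertiary as formal classes. Under sections 2.5.3 and 5.1.3 the tertiary class contains length of stay, alive and at home, DAAH90, angiographic success, therapeutic arteriography, MRI necrosis volume, adverse events, and haemodynamic and metabolic intolerance.

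Methods for these outcomes appear in two places. Section 5.2.3 says: "The analysis of hospital length of stay will be carried out by using linear regression models based on the same set of covariates". For the length-of-stay row Table 1 says: "Presented as median difference with 95% CI, using quantile regression". Section 5.2.3 also assigns "linear regression models for continuous data (DAAH90, daily dose of catecholamines, average daily urine output" and, for the binary outcomes, states: "Patients outcomes and treatment tolerance will be analyzed using logistic models for dichotomous data".

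**The concern.** A pre-specified plan protects an analysis made with the arms known only if it leaves one way to do that analysis. For several tertiary outcomes this SAP leaves two, and section 2.4 does not guarantee that the arms are still coded when the choice between them is made.

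At stake is the credibility of the non-fatal safety and tolerance results and of the length-of-stay and home-time results. A reader could not exclude that the reported model was picked after seeing which one suited milrinone or placebo. Opening the code earlier has no stated purpose, since the data are already locked.

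**Working it through.** **1. Text against table, outcome by outcome.**

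| Tertiary outcome | Section 5.2.3 | Table 1 |
|---|---|---|
| Hospital length of stay | linear | quantile (median difference) |
| DAAH90 | linear | quantile |
| Alive and at home, 3 and 6 months | logistic | quantile |
| Haemodynamic intolerance | logistic | log-binomial risk ratio |
| Dysnatraemia | logistic | log-binomial risk ratio |
| Daily catecholamine dose, urine output | linear | graph only |
| Angiographic success | ordinal | ordinal (agrees) |
| MRI necrosis volume | none given | quantile (single method) |

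Five outcomes have two rival models, and two more have a model in one place and only a graph in the other. For alive and at home, the table entry cannot deliver what the row asks for: the median of a yes/no variable is itself 0 or 1, so quantile regression does not estimate a difference in percentages.

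**2. Group size used below.** Section 2.3 gives 170 per group for 35% against 50%, two-sided 5%, 80% power. Check: [1.960 × √(2 × 0.425 × 0.575) + 0.842 × √(0.35 × 0.65 + 0.50 × 0.50)]² / 0.15² = (1.370 + 0.582)² / 0.0225 ≈ 169.3, rounded up to 170. The figure reproduces.

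**3. Linear versus quantile regression, length of stay.** Assumptions, not in the SAP: lognormal stay with log-mean 3.2 and log-SD 0.4 to 1.0, 170 per arm, no true difference, no covariates, shorter stay counted as favourable. Simulation, 10,000 replicates per row; each cell is the percentage of replicates whose 95% interval excludes zero.

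| log-SD | linear | median | either | both |
|---|---|---|---|---|
| 0.4 | 5.3 | 4.1 | 7.7 | 1.8 |
| 0.7 | 5.2 | 4.9 | 8.5 | 1.6 |
| 1.0 | 5.0 | 6.3 | 9.9 | 1.4 |

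The two models never excluded zero in opposite directions. An analyst who knows the arms and wants a favourable result reports whichever interval excludes zero on the favourable side, so the false favourable rate is about either/2. A false harmful interval survives only when both models show it, so its rate is about both/2.

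- log-SD 0.4: 7.7/2 ≈ 3.8 favourable (simulated 3.7); 1.8/2 = 0.9 harmful (simulated 1.0)
- log-SD 0.7: 8.5/2 ≈ 4.3 (simulated 4.3); 1.6/2 = 0.8 (simulated 0.8)
- log-SD 1.0: 9.9/2 ≈ 5.0 (simulated 5.1); 1.4/2 = 0.7 (simulated 0.7)

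With one fixed model the rate is about 5/2 = 2.5% in each direction.

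**4. Logistic versus log-binomial, tolerance outcomes.** Unadjusted Wald intervals, 170 per arm, no true difference, assumed event rates 20%, 35% and 50%, 20,000 replicates each. Either model excludes the null in 5.0%, 4.9% and 4.3% of replicates, identical to logistic alone. The choice does not affect whether the interval excludes the null. It does change how large the effect looks: at 35% and 50%, borrowed from section 2.3 purely as an illustration, the risk ratio is 0.50/0.35 = 1.43 and the odds ratio is (0.50/0.50)/(0.35/0.65) = 1.86.

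**The case against.** - **Section 2.4 sets an earliest time, not a schedule.** A reader might infer that all tertiary analyses will be run unblinded. The SAP does not say so, and the sponsor may well finish them on coded arms. This stands: the point is a missing guarantee.
- **The stakes are limited.** The SAP is to be public before lock, the data are locked before analysis, and the blind covers every outcome that receives a p-value. This stands too and sets the size of the point. It does not remove it, because section 3.1 requires intervals for every estimate and readers will see whether one excludes the null.
- **The root defect is the conflict between text and table.** An analyst with coded arms sees the same two intervals, so the 8 to 10% either-model rate is the same blinded or not, and it would be wrong to read it as an effect of unblinding. Coded arms remove only the ability to choose by direction; only a single named model removes the choice. The conflict also reaches secondary outcomes analysed before unblinding: GOSE and EQ-5D have proportional odds in section 5.2.2 and a linear model in Table 1. This stands, and it is why the fix has two parts.
- **Subgroup, sensitivity and per-protocol analyses.** It is tempting to count these as unprotected. They sit under the primary outcome in section 5.2.1, in section 5.2.4 and in the primary row of Table 1, so the natural reading places them before unblinding.

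**Conclusion.** The point holds as a gap of small consequence. Section 2.4 does not assure the blind for the tertiary, tolerance and adverse-event analyses, and for five tertiary outcomes the SAP allows two models.

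The only sized effect is for length of stay: about 4 to 5% false favourable and no more than 1% false harmful intervals under directional choice, against about 2.5% each with one fixed model. This rests on the assumed lognormal shape, 170 per arm, no covariate adjustment, and an analyst who does choose by direction, which nothing in the SAP suggests is intended. The same two models apply to DAAH90, but that outcome is bounded at 0 to 90 days and the percentages should not be transferred to it.

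A reader might infer that the safety and tolerance results have an inflated false-positive rate. The check does not support that: for haemodynamic intolerance and dysnatraemia the two models reach the same conclusion about the null and differ only in the effect measure reported. Nor is every tertiary outcome open to choice; angiographic success and MRI volume are not.

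**What to change.** Two changes, both before database lock.

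1. Replace the unblinding sentence in section 2.4 with: *The treatment code will be opened only after every pre-specified primary, secondary, tertiary and safety analysis has been run on coded arms and its programs and outputs have been archived.*
2. Reconcile section 5.2.3 with Table 1 so that each tertiary outcome has one named model and one effect measure. For alive and at home, use a model for a binary outcome. For daily catecholamine dose and urine output, state whether a model is fitted or only a graph is shown.

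The cost is one sentence, a table revision, and finishing the tertiary and safety programs before the code is opened. No further data or patients are needed. Both changes are needed: the first stops a choice by direction, the second removes the choice.

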2.5 Timing of outcome assessment

2.5.1 Primary outcome:

- a) Modified Rankin Scale (mRS) score [3 months]

2.5.2 Secondary outcomes:

- a) Modified Rankin Scale (mRS) score [6 months]; Glasgow Outcome Scale Extended (GOSE) [3 & 6 months]
- b) EuroQOL Quality of Life Scale 5-Dimension 5-Level (EQ-5D-5L) [6 months]
- c) Mortality [in hospital and 6 months]

2.5.3 Tertiary outcomes:

- a) ICU and hospital length of stays [in hospital]
- b) Angiographic success on CTA [D7 and D14 (if available)]
- c) Number of therapeutic arteriography [D14]
- d) Cerebral necrotic volume assess by magnetic resonance imaging (MRI) between 3 and 6 months following aSAH [6 months]
- e) Adverse events [study medication infusion, maximum 14 days]

 CHU ANGERS <small>CENTRE HOSPITALIER UNIVERSITAIRE</small>	 Statistical analysis plan	N° EudraCT 2019-002145-37 CT Number : 2024-515994-83-00 SAP V1.0 Date : 15/01/2026
---	--	---

3 Section 3: Statistical Principles

3.1 Confidence Intervals and P-values

The statistical uncertainty of all estimates will be expressed as two-sided 95% confidence intervals. A p-value will only be reported for all the primary and secondary outcomes. A p-value <0.05 will be considered significant.

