5.1 Outcome Definition

5.1.1 Primary outcome:

The primary endpoint is the proportion of good functional outcome (defined as a modified Rankin score (mRS) ≤ 2) at 3 months, obtained by centralized standardized phone interview of the patient or his/her relative.

Modified Rankin Score is rated as follow:

- 0 = No symptoms,
- 1 = No significant disability. Able to carry out all usual activities, despite some symptoms,
- 2 = Slight disability. Able to look after own affairs without assistance, but unable to carry out all previous activities,
- 3 = Moderate disability. Requires some help, but able to walk unassisted,
- 4 = Moderately severe disability. Unable to attend to own bodily needs without assistance, and unable to walk unassisted,
- 5 = Severe disability. Requires constant nursing care and attention, bedridden, incontinent,
- 6 = Death.

5.1.2 Secondary outcomes:

- a) Glasgow Outcome Scale Extended (GOSE) is obtained by centralized standardized phone interview of the patient or his/her relative done at 3 and 6 months. The GOSE is a global scale for functional outcome, categorized in 8 categories from 1 (death) to 8 (upper good recovery).
- b) EuroQOL Quality of Life Scale 5-Dimension 5-Level (EQ-5D) is a questionnaire is conducted at baseline, 3 and 6 months. It consists of a short and simple 5-part questionnaire and a visual analogue scale (VAS). It may be self-administered, completed by interview or via a proxy respondent, and is used to value and describe health states. The questionnaire data is reported as an index value - a continuous

 CHU ANGERS <small>CENTRE HOSPITALIER UNIVERSITAIRE</small>	 Statistical analysis plan	N° Eudract 2019-002145-37 CT Number : 2024-515994-83-00 SAP V1.0 Date : 15/01/2026
---	--	---

fractional outcome with boundaries between zero and one. Zero represents the worst health status and 1 the best. The EQ-VAS (visual analogue scale) is a self-administered visual scale in which respondents rate from 0 to 100 (worst and best state of health respectively) their perceived health-related quality of life at the time of response. In analyses including non-survivors, deceased patients will be given the lowest score. The EQ-5D will be analyzed as a variation from baseline at 3 and 6 months.

c) Mortality will be analyzed until 6 months.

5.1.3 Tertiary outcomes:

- a) ICU and hospital length of stays

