5.2 Analysis Methods

Unless otherwise specified, all analyses will be completed on the intention to treat population.

 CHU ANGERS <small>CENTRE HOSPITALIER UNIVERSITAIRE</small>	 Statistical analysis plan	N° EudraCT 2019-002145-37 CT Number : 2024-515994-83-00 SAP V1.0 Date : 15/01/2026
---	--	---

The characteristics at inclusion and the measures of patient assessments for each treatment arm will be described using percentages or means, standard deviations, medians and interquartile ranges, and compared using Khi-square tests or Student t tests for respectively categorical and continuous data. A summary of the proposed analyses is presented in Table 1.

5.2.1 Primary Outcome:

Primary analysis:

The main statistical analysis will be performed on the intention to treat population using a binomial logistic regression model including as covariates the treatment arm and the different stratification factors for randomization (the center, the initial WFNS score dichotomized as <3 vs ≥ 3 and the patient's consciousness at inclusion).

Secondary analysis:

As a secondary analysis, we will report absolute risk reduction using a proportional odds approach, using the Brant-Wald test at the alpha level of 5%, which may be more sensitive for detecting a shift over the entire spectrum of outcome (mRS 7-point ordinal scale).

Sensitivity analysis:

An other model will be proposed based on the ITT population, including in addition to the covariates already considered the level of consciousness and the delay before performing angiography (within 12 hours or not), and the interactions between these two covariates and the treatment arm, to assess a possible variation in the treatment effect according to the status on these two covariates

These two models will be performed on the per-protocol population as an evaluation of the robustness of their results. In any cases, the primary analysis results will be authoritative.

5.2.2 Secondary Outcomes:

- The analysis of the mRS, the extended GOS and the EQ-5D score at 3 and 6 months will be performed considering (ordinal) proportional odds models, based on the same set of covariates.
- The ICU mortality and 6 months mortality will be analyzed using Cox models based on the same set of covariates. The validation of these models will be evaluated by analyzing Schoenfeld residuals.

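### SAP 3.1 lets any secondary outcome with p<0.05 be called significant, with no error control across the six to nine secondary tests

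*SAP*

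**What the plan says.** Section 3.1 decides which outcomes get a p-value and sets a single threshold without separating primary from secondary: "A p-value will only be reported for all the primary and secondary outcomes. A p-value <0.05 will be considered significant". Tertiary outcomes get no p-value. The intervals are at the conventional level throughout: "The statistical uncertainty of all estimates will be expressed as two-sided 95% confidence intervals".

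The secondary outcomes are not listed the same way everywhere:

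- Section 2.5.2 has "Modified Rankin Scale (mRS) score [6 months]; Glasgow Outcome Scale Extended (GOSE) [3 & 6 months", which is three tests. It adds "EuroQOL Quality of Life Scale 5-Dimension 5-Level (EQ-5D-5L) [6 months", at that one time point, and mortality in hospital and at 6 months.
- Section 5.1.2 gives quality of life two time points: "The EQ-5D will be analyzed as a variation from baseline at 3 and 6 months". It describes both an index value and a visual analogue scale.
- Section 5.2.2 plans "The analysis of the mRS, the extended GOS and the EQ-5D score at 3 and 6 months" and names ICU mortality where sections 2.5.2 and Table 1 have hospital mortality.

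Two statements elsewhere come close to a hierarchy. Section 5.2.1 ends by giving the primary analysis precedence over the other models for 3-month mRS. Section 5.2.4 labels the subgroup analyses exploratory. Neither covers the secondary outcomes.

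**The concern.** Section 3.1 is a stated decision rule and not a silence that another document might fill. It gives a secondary outcome the same label, at the same threshold, as the one endpoint for which the trial was sized. If the primary result is neutral and one of functional outcome at 6 months, GOSE, quality of life or mortality falls below 0.05, a report that follows the plan to the letter may call that result significant. The same holds for an apparent harm. With several such tests, the chance that at least one crosses the threshold by luck is well above the 5% a reader would attach to the word.

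**Working it through.** **The plan's own design figure.** The SAP states no family-wise error rate. What can be reproduced is the sample size in section 2.3: 35% versus 50% favourable, two-sided 5%, power 80%, 1:1. With pooled variance under the null and mean proportion 0.425:

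n per arm = [1.960·√(2·0.425·0.575) + 0.842·√(0.35·0.65 + 0.50·0.50)]² / 0.15² = [1.370 + 0.582]² / 0.0225 ≈ 169.3, so 170 per arm and 340 in total, as stated. The primary test therefore uses the whole 5%, and none is set aside for secondary outcomes.

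**Number of secondary tests, k** (one per outcome and time point):

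- Section 2.5.2: mRS at 6 months (1) + GOSE (2) + EQ-5D at 6 months (1) + mortality (2) = 6.
- Sections 5.1.2 and 5.2.2, with EQ-5D at 3 and 6 months: 1 + 2 + 2 + 2 = 7.
- Index and EQ-VAS each tested at both times: 1 + 2 + 4 + 2 = 9. This is a possible reading; the SAP does not say it.

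**Independent tests.** The chance of at least one p<0.05 with no treatment effect is 1 − 0.95^k:

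- k = 6: 1 − 0.7351 = 26.5%
- k = 7: 1 − 0.6983 = 30.2%
- k = 9: 1 − 0.6302 = 37.0%

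**Correlated tests.** The outcomes overlap, so independence is a ceiling. Each test statistic was simulated as √ρ·C + √(1−ρ)·E, with C a standard normal shared by all tests and E a standard normal specific to each test. Any absolute value above 1.96 counted as significant (400,000 draws). The correlations are assumptions; the SAP gives none.

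| k | ρ = 0.3 | 0.5 | 0.7 | 0.8 | 0.9 |
|---|---|---|---|---|---|
| 6 | 24.1% | 20.7% | 16.3% | 13.8% | 10.8% |
| 7 | 27.0% | 23.0% | 17.8% | 14.8% | 11.6% |
| 9 | 32.6% | 26.8% | 20.3% | 16.7% | 12.3% |

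The range is 10.8% to 32.6%, and every cell is more than twice 5%. The errors split about evenly between false benefit and false harm: for k = 9 and ρ = 0.5, the chance of at least one error in a given direction is 13.5%.

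**With a neutral primary.** The table counts all trials with no effect, including the 5% in which the primary is also falsely significant. The chance of a significant secondary together with a non-significant primary is therefore at least the tabled figure minus 5 points: 10.8 − 5 = 5.8% at the lowest and 32.6 − 5 = 27.6% at the highest.

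**The case against.** The best defence is that the SAP already restrains inference in several ways. It has one primary endpoint at one time point, no p-values for tertiary outcomes, and subgroups labelled exploratory. It nowhere says that a secondary result can establish efficacy. On that view, significant in section 3.1 is a nominal label, and how to report nominal p-values on outcomes already ranked secondary is partly convention. This stands as a limit on severity: neither the main analysis nor the sample size depends on the point. It does not remove the point, because section 3.1 applies one label to both tiers and nothing tells a reader to discount it for the lower one.

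A reader might infer more than the SAP supports:

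- *That every secondary outcome will be declared significant.* The rule applies only to those with p<0.05.
- *That there are nine tests.* The SAP lists six or seven. Table 1 has a single EQ-5D row, and no section says that index and VAS are tested separately.
- *That the ordinal shift analysis of 3-month mRS is a further secondary test.* It is an analysis of the primary outcome, and section 5.2.1 already subordinates it.
- *That the false-positive chance is 37%.* This needs both nine tests and independence. In-hospital deaths are among the 6-month deaths, death is a category of both mRS and GOSE, and deceased patients receive the lowest EQ-5D score in analyses that include them.
- *That the primary conclusion is compromised.* It is a single test at 5%, and secondary testing does not alter that.

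Section 5.2.2 and Table 1 also name different models for some secondary outcomes, and Table 1 adds unadjusted ones. That could widen the choice of p-values, but the SAP does not say that each would carry a claim, so these models are not counted above.

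**Conclusion.** The point holds. Section 3.1 permits a claim of significance for any secondary outcome with p<0.05, and nothing in the SAP controls or qualifies that. With no treatment effect, the chance of at least one such claim is about 11% to 33% for six to nine tests, with 27% to 37% as the independence ceiling. The figures rest on assumed equal correlations of 0.3 to 0.9 and on the reading of k. The conclusion is the same at six tests and at the highest correlation considered. The defect concerns how secondary results may be described. It should be corrected, but it does not threaten the primary analysis.

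**What to change.** In section 3.1, reserve the term significant for the primary analysis of the primary outcome. State that secondary outcomes are reported as estimates with 95% confidence intervals, and that any p-value shown is unadjusted and not a basis for a claim. This takes about two sentences and changes no data, model or sample size. Section 2.4 has the SAP published before database lock, so the change is most credible if made by then.

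If a confirmatory secondary claim is wanted, two steps are needed. First, settle one list across sections 2.5.2, 5.1.2, 5.2.2 and Table 1: EQ-5D time points, index or VAS, and in-hospital or ICU mortality. Then test that list by Holm or in a fixed sequence, only if the primary is significant. Holm without that gate would still allow a claim after a neutral primary and would spend a second 5%. With seven tests, the smallest p-value would have to fall below 0.05/7 = 0.0071.

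The cost is that no secondary result can stand as a claim on its own. Under Holm a mortality difference, including a harmful one, is also harder to call significant. Mortality and other harm estimates would still be reported with their intervals, so no signal is hidden.
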